3.4 Selection of Study Population

The study will include subjects who completed activities through Day 11 in INS011-14-029 or Part A in INS011-15-054. The estimated maximum number of rollover subjects from these previous studies is as follows:

- INS011-14-029: 60 subjects
- INS011-15-054: 20 subjects

If all subjects are eligible for and elect to rollover into INS011-14-030, the population of this study will be a maximum of 80 subjects.

Each subject must satisfy all inclusion/exclusion criteria in Sections 3.4.1 and 3.4.2.

3.4.1 Inclusion Criteria

Subjects may be entered in the study only if they meet all of the following criteria:

1. Completed activities through Day 11 in INS011-14-029 or completed Part A in INS011-15-054.
2. Informed consent and assent (as applicable) of the subject and/or parent(s)/caregiver(s) in accordance with applicable laws, regulations, and local requirements.
3. Medically stable in the opinion of the Investigator.
4. Changes in background AEDs may occur during the study as discussed in Section 4.3. Care should be taken if patients are on other drugs metabolized by CYP enzymes.
5. A female subject is eligible to participate in the study if she is:
 - Premenarchal, or
 - Of childbearing potential with a negative serum pregnancy test at Screening (only for those subjects required to complete the Screening Visit) and a negative urine pregnancy test on Visit 2 (Day 1). If sexually active, she must fulfill 1 of the following requirements:
 - i) Complete abstinence from intercourse \geq 4 weeks prior to administration of the first dose of the investigational product, throughout the Treatment Period, and 4 weeks after completion or premature discontinuation from the investigational product, and agreement to use a double-barrier method if she becomes sexually active.

- ii) Use of acceptable methods of contraception throughout the study and 4 weeks after completion or premature discontinuation from investigational product. The acceptable method of contraception is double-barrier method (i.e., condom plus spermicide or a condom plus diaphragm).
6. A sexually active male subject must use acceptable methods of contraception throughout the study and for 4 weeks completion of study participation or premature discontinuation from investigational product. The acceptable methods of birth control are abstinence or double-barrier birth control (i.e., condom plus spermicide or a condom plus diaphragm).
7. In the opinion of the Investigator, subject and/or parent(s)/caregiver(s) are able to continue keeping accurate seizure diaries.

3.4.2 Exclusion Criteria

Subjects will not be entered in the study for any of the following reasons:

1. Experienced an anoxic episode related to study drug requiring resuscitation during their previous study.
2. Evidence of other clinically significant disease such as unstable hepatic, hematological, renal, cardiovascular, gastrointestinal, immunological, or pulmonary diseases or ongoing malignancies.
3. Compromised respiratory function or severe respiratory insufficiency.
4. Clinically significant abnormal laboratory values within the past 14 days, including:
 - LFTs such as albumin, direct bilirubin, total bilirubin, aspartate aminotransferase (AST), and alanine aminotransferase (ALT) ≥ 3 times the upper limit of normal (ULN).
 - The investigator may deem the subject eligible if in the opinion of the investigator, the clinically significant abnormal laboratory values are deemed to be acceptable and to not have an impact on subject safety.
5. Inadequate supervision by parent(s)/caregiver(s).
6. For appropriate subjects, an affirmative answer to queries regarding active suicidal ideation with some intent to act but without a specific plan or active suicidal ideation with specific plan and intent on the C-SSRS assessment at the Screening Visit. Subjects who have significant findings for suicidal ideation as assessed by the C-SSRS must be referred to the Investigator for follow-up evaluation.

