Objectives:	
To assess the long-term safety of Cannabidiol Oral Solution as an adjunctive treatment for subjects with treatment-resistant seizure disorders, including Lennox-Gastaut syndrome (LGS), Dravet syndrome (DS) or infantile spasms (IS).To establish the continued efficacy of Cannabidiol Oral Solution in maintaining seizure control in subjects with treatment-resistant seizures that previously completed INS011-14-029 or Part A (Visit 6) in INS011-15-054.To assess the global status of subjects taking Cannabidiol Oral Solution for an extended period of time determined by various qualitative assessments.To monitor for changes in plasma levels of Cannabidiol Oral Solution during long-term treatment of subjects with treatment-resistant seizure disorders, including LGS, DS or IS. 
Methodology: This is a multicenter, open-label study to assess the long-term safety and efficacy of Cannabidiol Oral Solution as adjunctive therapy for pediatric subjects with treatment-resistant seizure disorders, including LGS, DS, and IS. Subjects must complete 1 of the following studies to be eligible.
 
Activities through Day 11 in INS011-14-029.Activities in Part A through Visit 6 in INS011-15-054.
Eligible subjects will also be medically stable without new, clinically significant comorbidities since the Screening Visit in their previous study.	
Subjects should enroll in INS011-14-030 immediately upon completion of the Treatment Period in their previous study (to avoid interruption of the investigational product). If rollover does not occur within 2 weeks after completion of the Treatment Period in their previous study the subjects will need to complete a Screening Visit (Visit 1) to confirm continued eligibility. If rollover does occur within 2 weeks after completion of the Treatment Period in their previous study Day 11 for INS011-14-029. For subjects enrolling from INS011-15-054, there should be no interruption of greater than 2 weeks between completing treatment in INS011-15-054 and initiating treatment in INS011-14-030. All assessments for the previous study will be	

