3.0 INVESTIGATIONAL PLAN

3.1 Summary of Study Design

This is a multicenter, open-label study to assess the long-term safety of Insys' pharmaceutical Cannabidiol Oral Solution as adjunctive therapy for pediatric subjects with treatment-resistant seizure disorders, including LGS, DS and IS. Plasma levels of cannabidiol and its 7-OH metabolite and efficacy (seizure control and qualitative assessments of subject global status) will also be evaluated, though the latter will not be analyzed as endpoints.

Subjects must complete 1 of the following studies to be eligible for the current study:

- Activities through Day 11 in INS011-14-029
- Activities through Part A (Visit 6) in INS011-15-054.

Eligible subjects will also be medically stable without new, clinically significant comorbidities since the Screening Visit in the subject's previous study and satisfy the inclusion/exclusion criteria in Sections 3.4.1 and 3.4.2.

Subjects should enroll in INS011-14-030 immediately upon completion of the Treatment Period in their previous study (to avoid interruption of the investigational product). Rollover should occur within 2 weeks after completion of the Treatment Period in their previous study or when appropriate. A Screening Visit may be required for subjects that do not rollover within 14 days of completing their previous study.

In this study, subjects will be dosed as described below.

- Subjects who completed INS011-14-029 will initiate this study on the dose with which they were being treated previously, unless tolerability issues were observed for a particular subject.
- Subjects who completed Part A in INS011-15-054 will continue treatment with the dose at which they were being treated previously, unless tolerability issues were observed for a particular subject.

Subjects will receive twice daily oral doses of Cannabidiol Oral Solution as described in Section 4.1 for approximately 48 weeks or until the investigational product is successfully approved for marketing in the US (whichever occurs earlier), inclusive of their treatment on the previous study. For subjects that completed INS011-14-029, 48 weeks of treatment would be completed under this protocol. For subjects that participated in INS011-15-054,

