Physical examination and neurological examination ^k	X	X				X		X	X
Dispense (D), review (R), and collect (C) subject seizure and dosing diary ^l					D	D/R/C		R/C	
Dispense (D) and collect (C) study drug and review (R) dosing procedures		D/R	D/R/C	D/R/C	D/R/C	D/R/C		C	
Administer morning dose of study drug in the clinic		X				X			
AEs and SAEs	X	X	X	X	X	X		X	X
Blood draw for plasma levels		X			X	X		X	X

Assessments ^a	Visit 1 (14 Day Screening Period ^b)	Treatment Period						Final Visit / Discontinuation Visit ^d (Visit 10) Week 48 ±10 days ^e (if not conducted at a normally scheduled visit)	Follow-up Visit Two weeks after Final Visit / Discontinuation Visit (Visit 11) ±5 days
		Visit 2 (Day 1 ^c)	Visit 3 (Week 1) ±3 days	Visit 4 (Week 2) ±3 days	Visits 5, 6, & 7 Monthly: (Weeks 4, 8 & 12) ±7 days	Visits 8, 9, Quarterly: (Weeks 24 and 36) ±10 days ^d			
Investigator and Parent(s)/caregiver(s) CGI-S ^m	X	X			X	X		X	X
Investigator and Parent(s)/caregiver(s) CGI-I ^m					X	X		X	X
IPES ^{n, o}		X			X	X		X	X
VABS ^{n, p}		X						X	
C-SSRS ^q	X	X			X	X		X	X
Reminders for next visit ^s	X	X	X	X	X	X			

^a At Visits 2, 5, 6, 7, 8, 9 and 10 all assessments are to precede administration of the morning dose of the investigational product (i.e., the subject should arrive for their study visit without having taken the morning dose of the investigational product). See Section 5.1 for more details.

^b A Screening Period (Visit 1) will be required only for all subjects that do not rollover within 14 days of completing their previous study.

^c Visit 2 (Day 1) may occur simultaneously with Day 11 from INS011-014-029 or within 14 days of Visit 1 (Screening Visit) for INS011-14-030. All assessments (except vital signs) completed within 14 days prior to administration of the first dose of Cannabidiol Oral Solution in INS011-14-030 may be used for Visit 2 (Day 1) (to avoid repetition of procedures).

^d Subjects will receive two daily oral doses of Cannabidiol Oral Solution for approximately 48 weeks or until the investigational product is successfully approved for marketing in the US (whichever occurs earlier), inclusive of their treatment on the previous

study, unless they are discontinued due to a reason described in Section 3.4.3. After 12 weeks, study visits will be completed at a quarterly frequency; the definition of quarterly is every 12 weeks (e.g., Weeks 24 and 36).

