A brief neurological examination (mental status, cranial nerves, nystagmus, motor system, sensory system, reflexes, coordination, gait, and station) will be performed during other visits. All physical exams will also include an assessment of the subject's height and weight. Weight measurements at the quarterly visits may be used to calculate the subject's dose volume. Additional examinations may be performed at the discretion of the Investigator.

^l Seizure diaries will be collected to assess control of seizures (frequency, duration, and severity) for one week prior to each quarterly visit. In addition, timing of the administration of the drug and timing and contents of the meals will be collected.

^m For appropriate subjects will complete the CGI-I and CGI-S for themselves.

ⁿ For subjects who previously completed INS011-14-029, the IPES and VABS that are completed on Visit 2 (Day 1) of INS011-14-030 will serve as the baseline. Analysis will also be done using the Visit 2 (Day 1) data in INS011-14-030 as the baseline (see Section 8.2.2).

^o The IPES is validated for subjects who are 2 to 16 years of (developmental) age. Due to developmental delay characteristic of the study population, subjects through 18 years of chronological age will complete the IPES. Subjects enrolled from INS011-15-054 will be excluded from IPES evaluation.

^p The VABS is validated for use in subjects from birth to 90 years of age. To be conducted at Visits 2 and 10. Subjects enrolled from INS011-15-054 will be excluded from VABS evaluation.

^q The C-SSRS will only be completed for subjects for whom it is appropriate. The suggested age range for the pediatric version of the C-SSRS is from middle childhood (typically, around 7 years of age) through onset of adolescence (typically, through 11 years of age). However, in the face of cognitive delays, the tool can be suitable in older age groups. The appropriate adult version will be used in subjects 12 years of age and older. Subjects enrolled from INS011-15-054 will be excluded from C-SSRS scores evaluation.

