5.1 Screening Period (Visit 1)

Subjects that do not rollover within 14 days of completing their previous study (INS011-14-029) will be required to complete a Screening Visit. Subjects who enroll after participating in INS011-15-054 will not need to complete a Screening Visit if less than 14 days has elapsed between dosing.

The following procedures will be completed only after obtaining informed consent:

- Review of inclusion and exclusion criteria (see Sections 3.4.1 and 3.4.2)
- Record concomitant medications and concomitant procedures
- Obtain a 12-lead ECG
- Record vital signs (blood pressure, heart rate, respiratory rate, and temperature measurements)
- Draw blood samples for hematology and chemistry (fasting NOT required) and record whether subject was fasting at time of collection in the eCRF
- Obtain a urine sample for urinalysis
- Obtain a blood sample for serum pregnancy test in female subjects of childbearing potential
- Perform a complete physical examination (see Section 6.1.5.2), including height and weight

- Perform a neurological examination (see Section 6.1.5.2), including assessment for developmental capabilities
- Record demographic data
- Record medical and surgical history
- Record recent medication history including current AEDs, vitamins, herbal preparations, blood products, and over-the-counter drugs
- Record AEs and SAEs
- Administer Investigator CGI-S
- Administer parent(s)/caregiver(s) CGI-S
 - When appropriate, subjects will complete the CGI-S for themselves.
- Administer C-SSRS (if appropriate).

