 - The VABS is validated for use in subjects from birth to 90 years of age.
- Administer C-SSRS (if appropriate)
- Remind subject/parent(s)/caregiver(s) of next scheduled visit

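### Exclusion 6 tests suicidality only at a Screening Visit that subjects on the planned rollover route do not have

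*Protocol*

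**What the plan says.** Exclusion 6 in Protocol Section 3.4.2 applies to subjects for whom the C-SSRS is appropriate. It excludes those who report active suicidal thoughts with some intent, with or without a plan, "on the C-SSRS assessment at the Screening Visit". The synopsis carries the same criterion. Its second sentence, which sends significant C-SSRS findings to the Investigator, names no visit.

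Whether a subject has a Screening Visit depends on the gap after the previous study:

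- Table 1, footnote b: "A Screening Period (Visit 1) will be required only for all subjects that do not rollover within 14 days of completing their previous study". Sections 3.1 and 3.3 in places soften this to a possibility, but no section gives the visit to a prompt rollover.
- Section 3.1, on the planned route: "Subjects should enroll in INS011-14-030 immediately upon completion of the Treatment Period in their previous study".
- Section 5.1, on subjects from INS011-15-054: they "will not need to complete a Screening Visit if less than 14 days has elapsed between dosing".
- Synopsis, Methodology, on the same subjects: "there should be no interruption of greater than 2 weeks between completing treatment in INS011-15-054 and initiating treatment in INS011-14-030".

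Table 1 and Section 5.2.1 schedule the C-SSRS and the review of entry criteria at Visit 2 (Day 1). Table 1, footnote a, and Section 5.2 place all Visit 2 assessments before the morning dose. Table 1, footnote q, adds: "Subjects enrolled from INS011-15-054 will be excluded from C-SSRS scores evaluation".

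**The concern.** The criterion is tied to a visit that exists only for late rollovers. A subject who enters as planned goes straight to Visit 2 and gives C-SSRS answers there, but exclusion 6 does not refer to those answers. The same affirmative answer therefore excludes automatically on one entry route and not on the other.

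At stake are a safety rule that does not operate on the main route and an entry standard that differs by route. Literal wording counts here, because Section 3.4.3 requires the enrolment criteria to be applied to the letter, and the eligibility review at Visit 2 refers back to Section 3.4.2.

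**Working it through.** The point is textual, so the passages are set side by side first. The only arithmetic is a bound on size.

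**Which assessment can trigger exclusion 6?**

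| Entry route | Screening Visit? | C-SSRS before first dose in this study | Does exclusion 6 name it? |
|---|---|---|---|
| INS011-14-029, within 14 days | No | Visit 2 | No |
| INS011-14-029, later | Yes | Visit 1 and Visit 2 | Visit 1 only |
| INS011-15-054, gap under 14 days | No | Left out of C-SSRS evaluation | No |

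**Can earlier data fill the gap?** Table 1, footnote c, lets assessments from the preceding 14 days stand in for Visit 2. It does not let them stand in for Visit 1, so it creates no Screening assessment for a prompt rollover.

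**Could the criterion mean the previous study's Screening Visit?** Section 3.1 names the previous study when it means that study's Screening Visit, and exclusion 1 likewise refers to the previous study. Exclusion 6 has no such qualifier.

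**Are other rules written for both routes?** Yes:

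- Inclusion 5 asks for a serum pregnancy test at Screening where that visit is held, and also a urine test at Visit 2.
- Exclusion 4 uses a 14-day look-back that does not depend on a visit.
- Table 1, footnote k, places the full examination at whichever of the two visits comes first.

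No other exclusion criterion is tied to the optional visit.

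**Size.** Section 3.4 gives maxima of 60 subjects from INS011-14-029 and 20 from INS011-15-054: 60 + 20 = 80, which reproduces the stated total. Let p be the number of INS011-14-029 subjects who roll over within 14 days (not given, 0 to 60). Assume all 20 INS011-15-054 subjects enter with a gap short enough to need no Screening Visit.

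- Subjects without a Screening Visit = 20 + p.
- p = 0: 20/80 = 25%.
- p = 60: 80/80 = 100%.
- More than half (at least 41) requires p ≥ 41 − 20 = 21, and 21/60 = 35%.

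This counts subjects without the visit, not subjects whose entry the gap could affect. The latter are those among the p who are suitable for the C-SSRS. Sections 3.1 and 6.1.5.4 use clinical impression instead below age 7 and where developmental impairment makes the scale inappropriate. The number suitable is not given, so the affected group lies between 0 and 60. How many of them would answer affirmatively is not given either.

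**The case against.** The strongest reply is that subjects remain protected. A reader might infer that someone who reports suicidal intent at Visit 2 is eligible. The documents do not support that, because not triggering one exclusion does not establish eligibility:

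- Inclusion 3 requires the Investigator to judge the subject medically stable.
- Section 3.1 requires no new clinically significant comorbidity.
- The referral sentence in exclusion 6 applies at any visit.
- Section 3.4.3 allows withdrawal for safety.

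The Visit 2 answers are also due before dosing. This part of the reply stands: the loss is an automatic exclusion, not all oversight. These safeguards are discretionary, however, and do not replace a uniform entry rule. Suicide risk is also absent from the stopping criteria in Section 3.4.3, although SAP Section 9 lists it as a reason for discontinuation.

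A reader might also infer that the criterion fails for most subjects. The planned route points that way, but the documents count neither prompt rollovers nor subjects suitable for the scale. They describe a developmentally delayed population, in which many may not be suitable. A statement about most subjects is not supported.

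Finally, excluding a prompt rollover ends access to a treatment that the protocol aims not to interrupt. That is a real cost, and a reason for the sponsor to decide the rule deliberately rather than leave it to the wording.

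**Conclusion.** The inconsistency holds. On the route that the protocol plans for, exclusion 6 has no assessment to act on, while the relevant assessment and the eligibility review both take place at Visit 2 without a stated link to this criterion. For INS011-14-029 subjects who roll over promptly and are suitable for the C-SSRS, only Investigator discretion remains. They number at most 60; the actual figure cannot be derived from the documents. INS011-15-054 subjects fall outside the criterion on a second ground, because they are left out of C-SSRS evaluation.

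The conclusion rests on reading the Screening Visit as Visit 1 of this study, which the wording elsewhere supports. The study plans no hypothesis test, and no estimate is shown to change. The point concerns safety and consistent entry, and should be corrected on those grounds.

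**What to change.** Reconcile exclusion 6, in Section 3.4.2 and in the synopsis, with Table 1 and Section 5.2.1. The criterion should state which pre-dose C-SSRS governs entry in each case:

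- no Screening Visit is held;
- both Visit 1 and Visit 2 are held;
- an assessment from the preceding 14 days is used for Visit 2 under Table 1, footnote c.

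Inclusion 5 is a useful model because it deals with Screening and Visit 2 separately. Referring only to the subject's first visit would not settle the second case: a late rollover who is clear at Visit 1 and answers affirmatively at Visit 2 would still not meet the criterion.

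Which result should bar entry is for the sponsor to decide; the request is that the passages agree. The cost is a short wording change in two places by protocol amendment. No visit or scheduled procedure is added, since the C-SSRS is already listed at Visit 2. The downside is that a few more subjects may be excluded from continued access.

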3.4.3 Subject Withdrawal

All subjects are free to withdraw from participation in the study at any time, for any reason, specified or unspecified, and without prejudice to further treatment.

The criteria for enrollment are to be followed explicitly. If a subject who does not meet enrollment criteria is inadvertently enrolled, that subject should be withdrawn from the study and the Sponsor must be contacted. An exception may be granted in rare circumstances where there is a compelling safety reason to allow the subject to continue. In these rare cases, the Investigator must obtain documented approval from the Sponsor to allow the subject to continue in the study.

In addition, subjects will be withdrawn from the study in the following circumstances (i.e., stopping criteria):

- The Investigator decides that the subject should be withdrawn for safety
 - If the decision to remove the subject from the study is made because of an intolerable AE or a clinically significant laboratory value associated with the use of the investigational product, the investigational product is to be discontinued, appropriate measures taken, and the Sponsor notified immediately.
- Subject is unwilling to continue in the study and/or the subject or caregiver withdraw consent
- Lack of compliance with protocol
- Investigator or Sponsor stops the study for any reason
- Subject becomes pregnant
- Laboratory values demonstrate a subject serum ALT or AST level >3 times ULN (requires confirmation within 2 days)
- Laboratory values demonstrate a subject serum total bilirubin in excess of >2 times the ULN (requires confirmation within 2 days)
- Subject is enrolled in error
- Subject is lost to follow-up.
 - Lost to follow-up will be defined as a subject failing to attend planned study visits or to response to contacts by the study center staff contacts after

documented 2 attempts and for whom no other contact information is available.

Subjects who discontinue the study early will be asked to complete the Final Visit/Discontinuation Visit, with assessments to be completed as indicated in Table 1.

Subjects may elect to withdraw from study treatment with the possibility of completing remaining visits to allow for monitoring until end of study. All data taken through the subject withdrawing consent or the Investigator or Sponsor decision to discontinue the study, as well as data from the Final Visit/ Discontinuation Visit, will be collected for discontinued subjects.

Subjects who withdraw or are withdrawn from the study will not be replaced.

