6.1.4 Clinical Laboratory Evaluations

All clinical laboratory tests will be reviewed for results of potential clinical significance throughout the study. The Investigator will evaluate any change in laboratory values. If the Investigator determines a laboratory abnormality to be clinically significant, it is considered a laboratory AE; however, if the abnormal laboratory value is consistent with a current diagnosis, it may be documented accordingly.

The following laboratory tests will be assessed at the time points specified by Table 1.

- Hematology: complete blood count (CBC) with differential, including platelet count, neutrophils, lymphocytes, eosinophils, basophils, monocytes, hemoglobin, and hematocrit
- Serum chemistry: total protein, albumin, creatinine, blood urea nitrogen (BUN), uric acid, total bilirubin, direct bilirubin, alkaline phosphatase, FSH, AST, ALT, glucose, calcium, phosphorus, bicarbonate, chloride, sodium, and potassium
- Urinalysis: specific gravity, pH, color, and presence of white blood cells (WBCs), red blood cells (RBCs), and proteins
- β -hCG in urine (pregnancy test)

LFTs (e.g., albumin, direct and total bilirubin, AST, and ALT) will be closely monitored to identify any damage that could be induced by the investigational product.

Levels of FSH will be monitored as a potential surrogate outcome for gametocyte damage.

Laboratory values outside the reference limits suspected to be of any clinical significance will be repeated. Subjects in whom suspected clinical significance is confirmed will either not be included or if already enrolled will be followed until normalization or for as long as the Investigator considers necessary. Additional laboratory variables may be performed for safety reasons if judged appropriate by the Investigator. Further details are provided in the Laboratory Manual.

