8.3.4.1 AEs

The TEAEs are defined as AEs that first occur or worsen in severity after the first administration of the investigational product. Such AEs will be coded using the MedDRA coding dictionary and will be summarized by presenting the number and percentage of subjects having any AE, having an AE in each SOC, and having each individual AE as reported by PT. Furthermore, a summary for SAEs and summaries by severity and relationship to the investigational product will be presented by dose and overall. The most frequent (5%) AEs and drug related AEs will also be provided.

All percentages will be based on the number of subjects in the Safety Population.

In the summaries, AEs will be counted only once per subject. If a subject reports the same AE more than once, it will be counted with its worst severity and closest relationship to investigational product. Only those AEs that begin between start and end of study will be summarized.

The AEs will also be listed by subject and dose.

Subject death due to any cause and subjects with AEs leading to investigational product discontinuation will be listed and summarized by dose and overall.

The proportion of subjects that discontinue investigational product or experience dose interruption due to treatment emergent AEs will be summarized by dose and for all subjects.

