9. DISPOSITION AND WITHDRAWALS

All subjects who provide informed consent will be accounted for in this study.

Subject disposition and withdrawals, and protocol violations, including inclusion and exclusion criteria will be presented for the ENR set.

The table will summarize the following information:

- Number of subjects screened
- Number of screen failures - overall and by following reasons:
 - subject did not meet eligibility criteria
 - Withdraw informed consent
 - Subject died
 - Other
- Number of treated subjects (SAF)
- Number of subjects in the PK
- Number of subjects who completed study including follow-up
- Number of subjects who discontinued from treatment (overall and by reasons)
- Number of subjects with early discontinuation from study (overall and by reasons)

For both discontinuation from treatment/study the reasons are as follows:

- Inadvertently enrolled (enrollment criteria not met)

Document: C:\Users\q832483\Documents\Insy CSR\Pending\Ready for QC\New folder\Statistical Analysis Plan.docx
Author: [REDACTED] Version Number: V1.0 Final
Version Date: 04APR2017

Template No: CS_TP_BS016 – Revision 3
Effective Date: 01May2012

Reference: CS_WI_BS005

- Investigator decision
- Adverse Event
- Subject withdrew consent
- Lack of protocol compliance
- Subject attempted suicide or is at risk of suicide
- Sponsor decision
- Subject becomes pregnant
- Abnormal laboratory values
- Lost to follow-up
- Death
- Other

The following important (clinically) protocol deviations, as identified in the clinical trial management system (CTMS), will be summarized:

- Administrative Criteria
- Eligibility and Entry Criteria
- IP Compliance
- Informed Consent
- Laboratory Assessment Criteria
- Serious AE Criteria
- Study Procedures Criteria
- Regulatory or Ethics Approvals Criteria
- Visit Scheduled Criteria
- Other Criteria

Supportive listings will also be provided:

- Allocation to treatment
- Protocol deviations
- Subjects eligibility criteria

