17.1.3. TEAEs LEADING TO DISCONTINUATION OF STUDY MEDICATION

TEAEs leading to permanent discontinuation of study medication will be identified by a response of "Dose discontinued" for the "Action taken with study medication" question on the AE page of the eCRF. For TEAEs leading to discontinuation of study medication, summaries of incidence rates (frequencies and percentages) by SOC and PT will be prepared. Such TEAEs will also be listed separately.

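### Withdrawals under the numeric liver criteria may be missing from the table of adverse events leading to discontinuation

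*Protocol*

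**What the plan says.** Five places bear on this.

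- **Protocol 3.4.3** has two numeric liver criteria: "Laboratory values demonstrate a subject serum ALT or AST level >3 times ULN (requires confirmation within 2 days" and "Laboratory values demonstrate a subject serum total bilirubin in excess of >2 times the ULN (requires confirmation within 2 days". They are separate bullets from "The Investigator decides that the subject should be withdrawn for safety", whose sub-bullet covers removal "because of an intolerable AE or a clinically significant laboratory value associated with the use of the investigational product".
- **Protocol 6.1.4** makes a laboratory abnormality an AE when the investigator considers it clinically significant. It then adds an exception: "if the abnormal laboratory value is consistent with a current diagnosis, it may be documented accordingly".
- **SAP 9** uses one list of reasons for stopping treatment and for leaving the study. "Abnormal laboratory values" stands beside Adverse Event and Investigator decision as its own entry. No rule says which to choose when several apply.
- **SAP 17.1.3** builds its table from the AE page: "TEAEs leading to permanent discontinuation of study medication will be identified by a response of" Dose discontinued to the action-taken question.
- **Protocol 8.3.4.1** promises the matching result: "The proportion of subjects that discontinue investigational product or experience dose interruption due to treatment emergent AEs will be summarized".

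**The concern.** The trigger for withdrawal is a number, while the trigger for an AE record is a judgement. Nothing in either document joins the two. A confirmed liver elevation can therefore end treatment without producing the AE-page entry on which the discontinuation table depends.

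Long-term safety is the primary objective (SAP 2.1), and discontinuation for adverse events is one of its main tolerability results. The liver criteria are the only laboratory stopping criteria in 3.4.3 with a numeric threshold. A missing AE record can only lower the count in this table, so any error favours the product.

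Elsewhere the SAP resolves doubt the other way. Missing intensity becomes severe and missing relationship becomes related (SAP 7.2), and unclear timing becomes treatment-emergent (SAP 17.1). Here, the absence of an AE entry means that the subject is not counted.

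**Working it through.** The plan gives no figure for this quantity, so there is none to reproduce. The check follows one subject through the rules and then sizes the possible loss.

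**Step 1. A confirmed ALT, AST or bilirubin value meets a 3.4.3 criterion and the subject is withdrawn.**

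| AE page | Disposition reason (SAP 9) | In the SAP 17.1.3 table? |
|---|---|---|
| Treatment-emergent laboratory AE, action Dose discontinued | Any | Yes |
| Laboratory AE, another action entered | Any | No |
| No AE: judged not clinically significant, or put down to a current diagnosis | Any; none is prescribed | No |

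The disposition reason does not decide the outcome. A subject filed under abnormal laboratory values is counted if the first row applies. The gap is the second and third rows.

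**Step 2. Is the third row realistic?** Exclusion criterion 4 (Protocol 3.4.2) lets the investigator enrol a subject with liver tests at or above 3 times ULN if the values are judged acceptable and without effect on safety. Protocol 6.1.1.1 expects liver-enzyme rises from altered metabolism of background antiepileptic drugs, and Protocol 1.2 lists liver failure among the safety issues of valproic acid. This does not show how often an AE would go unrecorded. It shows that attribution to something else is foreseeable.

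**Step 3. Where else would the case appear?**

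- The SAP 9 disposition table shows it under whichever reason was chosen.
- The SAP 14 exposure listing gives the reason for ending treatment. The SAP 14 dose-modification table offers only adverse event, lack of efficacy, PK result and other, so a liver stop without an AE would fall under other.
- The SAP 17.3.1 summary uses the same liver thresholds, but by time point and without a link to discontinuation. SAP 6.3 keeps unscheduled values out of by-visit summaries, so a value found only between visits may be absent.
- SAP 17.3 lists all laboratory data with abnormal values flagged.

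No planned output combines AE-page discontinuations with the other safety reasons and counts each subject once.

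**Step 4. Size.** The maximum N is 60 + 20 = 80 (Protocol 3.4 and 8.1).

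- Each missed subject: 1/80 = 1.25 percentage points.
- The documents give neither the share r meeting a liver criterion nor the share f of those with no discontinuing AE, so both are assumed. Expected number missed = 80 × r × f.
- r = 5%, f = 50%: 80 × 0.05 × 0.50 = 2 subjects, or 2.5 points. The chance of missing at least one is 1 − (1 − 0.025)^80 = 0.87.
- r = 15%, f = 50%: 80 × 0.15 × 0.50 = 6 subjects, or 7.5 points.
- f = 0: no loss, whatever r is.

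Over r from 2% to 15% and f from 0% to 50%, the expected loss runs from 0 to 6 subjects (0 to 7.5 points).

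**The case against.** The best case for the plan is that little can escape. An AE is any untoward occurrence, causal or not (Protocol 6.1.1). All AEs are to be recorded, whatever their severity, with the action taken (6.1.2). Rises in liver enzymes head the list of AEs to watch for (6.1.1.1). A repeat-confirmed value that ends participation will often be judged clinically significant, and it is then an AE under 6.1.4. Cases without an AE record remain visible in the outputs named above, and with at most 80 subjects a reader could find each one. This stands as a limit on the size. It does not close the gap, because no sentence makes the AE record mandatory and the reader would have to assemble the total by hand.

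Three stronger readings are tempting, and the documents support none of them.

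- A reader might infer that these subjects *are* filed outside Adverse Event and that discontinuations *are* under-counted. SAP 9 assigns no reason, Adverse Event is equally available, and the table does not use that field.
- A reader might extend the point to every safety withdrawal, including investigator decisions and suicide risk. The situations that 3.4.3 names under the investigator's decision are an intolerable AE, or a clinically significant laboratory value, which 6.1.4 makes an AE apart from its exception. Protocol 6.1.5 applies a similar rule to other safety findings, and a suicide attempt meets the general AE definition.
- A reader might blame the lack of a liver term in SAP Appendix 2. That is a list of AE preferred terms, so a liver term would not retrieve a case with no AE record.

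**Conclusion.** The point holds as a possible under-count confined to withdrawals under the ALT/AST and bilirubin criteria. The plan allows such a withdrawal to be absent from the TEAE-discontinuation table and provides no unduplicated count of safety-related discontinuations. The cases are not hidden, because they appear in disposition and, for scheduled-visit values, in the liver-test summary.

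The size cannot be determined from the documents. It is 1.25 points per missed subject at N = 80, and more per subject if fewer enrol. It is zero if every liver-criterion stop carries a treatment-emergent AE with action Dose discontinued. The 0 to 7.5 point range rests wholly on assumed rates. This is an inexpensive improvement to the reporting of a primary safety study and does not show that its result would be wrong.

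**What to change.** 1. **SAP 17.1.3:** add one row and a listing that count each subject once if the AE-page action is Dose discontinued, or if the end-of-treatment reason is Adverse Event, Abnormal laboratory values, suicide attempt or risk, or Death. List Investigator decision cases separately, because the SAP does not split them into safety and other. Keep the existing TEAE table as it is.
2. **Protocol 6.1.4:** state that a confirmed laboratory value that triggers withdrawal under 3.4.3 is recorded as an AE whatever its attribution, with the action actually taken. Dose discontinued should not be made the compulsory entry. Laboratory samples are also drawn at Visits 10 and 11, when dosing may already have ended, and the entry could then be false.

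The stopping thresholds stay as they are.

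The cost is one table row, one listing and one protocol sentence. The end-of-treatment reason is already planned for a listing (SAP 14). Protocol 8.2.1 allows changes in statistical methods before database lock to be documented in the SAP without an amendment; the 6.1.4 sentence changes the protocol text itself. The reported discontinuation figure may become less favourable.
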